### Version date:(Version 4,11/13/2023)

## E. Research-related expenses

	Project Name	Explanation	Unit price	Quantity	Total Price	Notes
i. Business expenses	1.Research manpower costs (please consult the Human Resources Department for related insurance expenses)	
 
(1) Dedicated Personnel (Limited to Individual Project Applications) : Remuneration for work (including year-end bonus) is the responsibility of the employer for labor insurance and health insurance. The employer is also responsible for labor retirement benefits (insured at 6% of salary)
 
(2) "Part-time staff (must be current students) : Work remuneration College graduates
 
Master's students
 
Other : Labor and health insurance borne by the employer Employer's contribution to labor retirement (insured salary 6%)
 
(3) Temporary worker : Remuneration for work Labor and health insurance borne by the employer
 
Employer's contribution to labor retirement (insured salary 6%)
 
	4,400 936 26 1,286 270	12 12 12 12 12 12	52,800 11,232 312 15,432 3,240	Hourly wage \$176 25 hours per month. Subtotal: 83,016 NTD
	2. Animal testing			Subtotal :	83,016	
	expenses			Subtotal :		
	3. Consumables, Supplies, Books, and Miscellaneous	Participant Allowance Heart rate variability rental	1,000 9,000	600 12	600,000 108,000	
	expenses	expenses for equipment Computer peripheral consumables expenses: Toner	5,000	1	5,000	
		cartridge, ink cartridge, printer photosensitive drum/photoreceptor, special printing paper, etc.	3,984	1	3,984	
		Miscellaneous: Postage and				
		telecommunication expenses, printing expenses,				
1		photocopy paper expenses, photocopying				
1		expenses, binding expenses, stationery expenses,				
		poster production expenses, computer data				

version date + (v	ersion 4,11/15/2025)			
	statistical expenses, computer data analysis			
	expenses, thesis submission fees, thesis			
	publication fees, slicing, embedding, and			
	immunostaining expenses			
		Subtotal :	716,984	
ii. Research				
equipment exp (According to reg				
books, computers				
peripheral equipm				
not eligible for su	bsidies.	Subtotal :	0	
The necessity of r	nedium			
and large-sized				
instruments will b				
determined by the				
Research Departn				
applications for the unified use will be				
submitted)				
suominud)			800,000	
Total				

### F. Project Abstract

Please provide a brief overview of the key points of this project within 500 words and customize keywords based on the nature of the project.

Patients with disorders of gut-brain interaction (DGBI) often present gastrointestinal symptoms that do not show noticeable irregularities in standard examinations. However, due to unclear causes and a high prevalence rate, this condition often exerts a profound impact on the physical and mental health of patients. The scope of DGBI encompasses conditions such as laryngopharyngeal reflux, functional dyspepsia, and irritable bowel syndrome. Previous research has confirmed that in patients with DGBI, their autonomic nervous system exhibits an imbalance, characterized by decreased parasympathetic activity and dominant sympathetic activity. Diaphragmatic breathing helps reduce the respiratory rate and can stimulate parasympathetic activity while suppressing sympathetic activity. Hence, it is now officially recommended as an effective adjunct therapy for relieving symptoms of gastroesophageal reflux. Accordingly, this study plans to implement a randomized controlled trial, introducing diaphragmatic breathing to patients with DGBI who exhibit normal results in objective examinations. This work allows evaluate changes in their psychophysical symptoms before and after treatment, as well as alterations in the autonomic nervous system.

**Key words**: disorders of gut-brain interaction, psychophysical symptoms, diaphragmatic breathing, autonomic nervous system

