**Figure 3.** During the high-resolution esophageal impedance measurement period after a 20-minute meal, under random allocation, both the healthy control group (a) and the patient group (b) demonstrated a significant reduction in the number of reflux events with diaphragmatic breathing. In contrast, the sham (normal) breathing group showed no significant difference in reflux events.

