### **Research Methods**

### Participant

The trial is expected to last for 1 year, with a research period ending on December 31, 2024. It aims to recruit 600 participants, including 150 healthy volunteers to be solicited through advertisements. Additionally, 150 participants with Laryngopharyngeal Reflux (LPR) will be recruited from the Gastroenterology Outpatient Department, along with 150 participants with Functional Dyspepsia (FD) and 150 participants with Irritable Bowel Syndrome (IBS). The inclusion and exclusion criteria for participants are as follows :

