### **Research Process Diagram**

### **Finish experiment**

### **Research Steps**

The subjects who meet the inclusion criteria of this study will undergo an initial assessment of heart rate variability and psychosomatic symptoms after enrollment. Subsequently, a two-week

experiment will be conducted, during which the subjects will receive one session of diaphragmatic breathing training by the researchers. After the guided training, the subjects will undergo another assessment of heart rate variability. In the first week, participants will engage in self-practice of the instructed content twice daily, each session lasting 5 minutes, and will record a weekly diaphragmatic breathing diary.

After the first week, subjects will undergo another assessment of heart rate variability and psychosomatic symptoms. In the second week, participants will continue daily self-practice with two sessions of instructed content, each lasting 5 minutes, and will maintain a diaphragmatic breathing diary. Following the second week, subjects will undergo a final assessment of heart rate variability and psychosomatic symptoms, completing the experiment.

Researchers recommend spending approximately 15 minutes on diaphragmatic breathing training, 15 minutes on measuring heart rate variability, and approximately 20 minutes for questionnaire completion. The measurement of heart rate variability utilizes a non-invasive device called "LEADTEK" portable electrocardiogram recorder (Ministry of Health and Welfare Medical Device Manufacturing License No. 006972). If participants have any questions or concerns during the abdominal breathing training process, they are encouraged to contact the researchers.

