### **Statistical Analysis**

If a continuous variable follows a normal distribution, it is represented by the mean and standard deviation; if it does not follow a normal distribution, it is represented by the median and interquartile range. The treatment effectiveness is presented as the improvement percentage based on the pre- and post-treatment sleep habit questionnaire, depression questionnaire, anxiety questionnaire, stress questionnaire, digestive symptom questionnaire, and irritable bowel syndrome questionnaire. The efficacy of diaphragmatic breathing was assessed using a Chi-squared test to compare percentages. A P-value less than 0.05 was considered statistically significant. The statistical analysis software used is SPSS 19 (SPSS, Inc, Chicago, IL, USA).

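### The Project Abstract declares a randomized controlled trial, but the readable methods text gives no allocation step, arms or comparator for the symptom hypothesis

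*Protocol*

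**What the plan says.** - **Design label.** Section F (Project Abstract) says that "this study plans to implement a randomized controlled trial". The sentence after it describes the evaluation as one that will "evaluate changes in their psychophysical symptoms before and after treatment".
- **Sample.** The Participant section says: "It aims to recruit 600 participants, including 150 healthy volunteers to be solicited through advertisements". The other 450 are patients: 150 with laryngopharyngeal reflux (LPR), 150 with functional dyspepsia (FD) and 150 with irritable bowel syndrome (IBS). No cohort is divided further and no allocation ratio is given.
- **Procedures.** Research Steps begins: "The subjects who meet the inclusion criteria of this study will undergo an initial assessment of heart rate variability and psychosomatic symptoms after enrollment". A two-week period follows in which "the subjects will receive one session of diaphragmatic breathing training by the researchers". Repeat HRV, daily practice with a diary, and assessments after each week complete the experiment. No other path is described.
- **Analysis.** Statistical Analysis says: "The treatment effectiveness is presented as the improvement percentage based on the pre- and post-treatment sleep habit questionnaire", followed by the other questionnaires. Its next sentence assesses efficacy with a chi-squared test on percentages and does not name the groups compared.
- **Hypotheses.** Hypothesis 2 and its parts 2-1 (LPR), 2-2 (FD) and 2-3 (IBS) expect symptoms to improve with breathing. None names a comparator.

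**The concern.** A reader who follows Participant, Research Steps and Statistical Analysis as written would train the enrolled subjects, measure them before and after, and report the change. That is an uncontrolled before-after study, yet the abstract would have it reported as a randomized controlled trial.

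The label matters because the aims lean on it. Research Purpose sets out to confirm whether breathing improves symptoms in patients, and the section on clinical significance speaks of efficacy and mechanism. In symptom-defined disorders scored by self-report, change over two weeks also reflects natural course and expectation. Without a concurrent comparator, that part of the change cannot be separated from an effect of breathing.

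**Working it through.** **1. Reproduce the sample size.** Inputs from the Participant section: 150 healthy, 150 LPR, 150 FD, 150 IBS. 150 + 150 + 150 + 150 = 600, the stated total. The expenses table in section E also budgets 600 participant allowances. Health status or diagnosis therefore uses every place, and any comparator would have to sit inside the cohorts.

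**2. Look for a comparator in the readable text.**
- *Healthy cohort.* Its inclusion criteria require no gastrointestinal symptoms, so it has none to improve. Hypothesis 1-1 concerns the effect of breathing in healthy subjects, so it is exposed too. It is recruited by advertisement, not by randomization. It cannot be the comparator for Hypothesis 2.
- *The other disease cohorts.* Research Steps distinguishes no cohort, so all are on the training path. A chi-squared test across LPR, FD and IBS would ask whether improvement differs by diagnosis, not whether breathing causes improvement.
- *Sham breathing.* The only random allocation and sham group are in the Figure 3 caption, where "the sham (normal) breathing group showed no significant difference in reflux events". That caption reports a cited earlier trial.
- *A randomized split within cohorts.* None is described.

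**3. Reach.** Hypothesis 2 has three parts and all three are affected. Patients: 3 × 150 = 450; 450/600 = 75% of the sample.

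**4. Size of any bias.** It cannot be computed, because the protocol gives no expected improvement rate, SD or retest correlation. As an illustration only, assume that breathing has no effect and that scores drift by δ SDs of the change score. A paired test on n = 150 at two-sided 0.05 then shows significant improvement with probability Φ(δ√150 − 1.96):
- δ = 0.1: 0.231
- δ = 0.2: 0.688
- δ = 0.3: 0.957

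The drifts are assumptions, and the paired test is not the protocol's chi-squared test. The figures show only how readily drift could pass for effect at this cohort size.

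**5. What a randomized split would leave.** Assume 1:1 allocation within a cohort, so 150/2 = 75 per arm. With p̄ the mean of the two rates, power = Φ{[|p₁ − p₂| − 1.96√(2p̄(1 − p̄)/75)] / √[(p₁(1 − p₁) + p₂(1 − p₂))/75]}. For 30% v 50% improved: (0.20 − 1.96 × 0.0800)/0.0783 = 0.55, giving power 0.709. For 30% v 45% it is 0.475, and for 30% v 40% it is 0.248. These rates are assumptions as well.

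**The case against.** The strongest reply is that the arms may be defined where this text cannot be read. The content of the Research Process Diagram is lost except for its last box, a flow diagram is a usual place to show allocation, and the pages before section E are not available. The background also gives the lack of randomized evidence in other DGBI as the gap to be filled, so the label may be intended. This stands. A reader might infer that the study has no control group; the documents do not support saying so outright.

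Second, several features fit a randomized trial. Change from before to after treatment is an ordinary trial outcome. Cohorts of 150 can be recruitment strata, each randomized internally. A chi-squared test on percentages normally needs at least two groups, which hints at a between-group comparison. All of this stands, so the pre/post wording alone proves nothing. But the test's groups are unnamed, and the only ones that can be read are the cohorts.

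Third, if the diagram does show arms, Research Steps would be incomplete rather than contradictory. That is fair: the fault would then be that the prose does not say which arm it describes.

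A reader might also infer regression to the mean in LPR from the entry rule of an RSI total above 13. That requires the screening score to serve as the baseline score, which the protocol does not state, so the point does not rest on it.

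What does not stand is leaving the matter to a statistical analysis plan. Allocation and comparator are part of the study's conduct, and an analysis plan cannot supply a control group that the procedures do not run.

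**Conclusion.** The concern holds in conditional form. The abstract's label is not carried into the readable Participant, Research Steps and Statistical Analysis text, which must be corrected whichever design is intended. If arms are defined in the diagram or the front pages, the defect is prose that does not identify its arm and a test that does not name its groups. If they are not, Hypothesis 2 has no comparator, and an uncontrolled result would be reported as randomized evidence of efficacy. The affected part is all three components of Hypothesis 2 and 450 of 600 participants. No size of bias is claimed. Confidence is moderate, because the unreadable material could settle which case applies.

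**What to change.** Reconcile the Project Abstract, Participant, Research Steps and Statistical Analysis sections by one of two routes.

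- **If randomized arms are intended:** state the allocation and the comparator in Participant and Research Steps, limit the training text to the arm that receives it, and name the randomized arms as the groups compared in the efficacy test. The cost is size: the cohorts already use all 600 places, so each arm within a cohort holds fewer than 150 (75 if 1:1), and the sample size should be justified on that basis.
- **If not:** remove the randomized controlled label from the abstract and describe an uncontrolled before-after study in one healthy and three disease cohorts. Restate Hypothesis 2, the aim in Research Purpose and the efficacy statement under clinical significance as within-group change that cannot be attributed to breathing alone. This is a change of wording only; the cost is a weaker claim.

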### G. Background and Objectives of the Research Project

Please elaborate on the background, objectives, significance, as well as the domestic and international research status related to this research project. Provide a review of the important references and literature relevant to this project.

### **Research Background**

### Disorders of gut-brain interaction, DGBI

Functional GI Disorders, currently referred to as Disorders of gut-brain interaction (DGBI), encompass gastrointestinal symptoms for which, upon objective examination, no organic cause can be identified. Nevertheless, patients still endure the distressing symptoms related to the gastrointestinal tract. The symptoms of gastrointestinal disorders are diverse, encompassing the esophagus, stomach, small intestine, and large intestine. The origin of these symptoms is complex and includes factors such as imbalance in the intestinal microbiota, changes in mucosal immune function, alterations in signaling around the intestinal area, and dysregulation of central nervous system control over intestinal signaling and motor function (Figure 1). If it affects the upper digestive tract, it may lead to symptoms such as upper abdominal pain and bloating; these symptoms are referred to as Functional Dyspepsia (FD). If it affects the lower digestive tract, there may be issues such as abdominal pain, diarrhea, and constipation; this condition is classified as Irritable Bowel Syndrome (IBS). The recent research we have conducted indicates that among patients with symptoms of gastroesophageal reflux disease (GERD), only about 20% show pathological evidence of reflux. However, among those with throat reflux symptoms (such as hoarseness, sensation of a lump in the throat, chronic cough, and frequent throat clearing), their Esophageal Hypervigilance and Anxiety Scale (EHAS) scores are higher compared to individuals without throat reflux symptoms, even in the absence of pathological reflux evidence. These DGBIs (Functional Gastrointestinal Disorders) do not respond well to conventional gastrointestinal medications, so sometimes it is necessary to supplement treatment with neuromodulators from the field of psychosomatic medicine.

# The Relationship Between the Autonomic Nervous System and the Disorders of gut-brain interaction

The gastrointestinal tract is governed by the intrinsic Enteric nervous system (ENS) and the extrinsic Autonomic nervous system (ANS). ENS can automatically regulate the gastrointestinal tract, while the Central Nervous System (CNS) interacts with the Enteric Nervous System (ENS) through the Autonomic Nervous System (ANS), providing external neural input to regulate and control gastrointestinal functions (Figure 1).7-9 The Parasympathetic Nervous System (PNS) or Sympathetic Nervous System (SNS), either singly or both, may encounter disruptions, leading to impaired communication between the gastrointestinal tract and the brain, subsequently resulting in Functional Gastrointestinal Disorders (FGID). The upper gastrointestinal tract (esophagus, stomach, small intestine, ascending colon) is innervated by the parasympathetic nervous system, with the main source being the Vagus nerve. In contrast, the lower gastrointestinal tract (transverse colon, descending colon, sigmoid colon, external anal sphincter muscles) receives parasympathetic innervation from the Lumbosacral spinal cord's pre-ganglionic neurons, primarily originating from the S1-S4 segments. Most research reports consistently find that patients with Functional Gastrointestinal Disorders (DGBI) exhibit reduced parasympathetic nervous system activity and an increased dominance of sympathetic nervous system activity. These findings align with the autonomic control of gastrointestinal motility: activation of the parasympathetic nervous system enhances E6A0021096-10 Total 30 Page, Page 16

gastrointestinal motility, while activation of the sympathetic nervous system inhibits gastrointestinal motility.

**Figure 1**. The possible etiology of DGBI includes microbial imbalance in the intestinal tract, changes in mucosal immune function, alterations in peripheral signaling around the intestines, and dysregulation of central nervous system control over intestinal signaling and motor function. Among these factors, the autonomic nervous system plays a crucial role as a communication bridge between the brain (central) and the gastrointestinal tract (peripheral).

### Heart rate variability

Early studies have shown that through Heart Rate Variability (HRV), the autonomic nervous system (ANS) can be assessed to evaluate the functional status of the gastrointestinal system. The reason is that the autonomic nervous system (ANS) includes both the parasympathetic and sympathetic nervous systems, which regulate the outgoing and incoming fibers of the gastrointestinal tract through the nucleus tractus solitarius (NTS). The NTS also contains other autonomic neural control over organs whose functions are regulated by the central nervous system (CNS) through the ANS, such as cardiovascular functions. Therefore, the central nervous system (CNS) also influences cardiovascular function through the autonomous regulation of sensory inputs from the gastrointestinal tract. This is because there is interaction between subnuclei in the nucleus tractus solitarius (NTS), regulating the rhythm or variability of the heart, known as heart rate variability (HRV). In addition to assessing the autonomic nervous system (ANS), the analysis of heart rate variability (HRV) has also been found to be clinically effective in evaluating the therapeutic efficacy of the autonomic nervous system for disorders of gut-brain interaction (DGBI). HRV parameters can be used as biological markers for assessing treatment outcomes. For example, electrical stimulation therapy is an emerging treatment method for these diseases. Numerous studies consistently demonstrate that neurostimulation therapy improves symptoms of DGBI by enhancing autonomic nervous system dysfunction assessed through HRV.

HRV is influenced by two main physiological mechanisms: the first originates from the complex and dynamic interplay between the sympathetic and parasympathetic nervous systems; the second arises from regulatory mechanisms controlling heart rate, including RSA, blood pressure reflexes, and rhythmic variations in vascular tone. HRV is primarily applied in the assessment of the autonomic nervous system (ANS). As follows : 

### 1. Time Domain Indicator

- Root mean square of successive differences (RMSSD): RMSSD reflects the variability between heartbeats and is primarily used to estimate the changes in parasympathetic nervous system activity, especially the vagus nerve, in Heart Rate Variability (HRV). RMSSD is considered to be an important indicator of HRV. The RMSSD values over a 24-hour period are highly correlated with the difference in adjacent normal heartbeat intervals exceeding pNN50 and high-frequency (HF) power. The lower RMSSD values are positively correlated with the risk assessment of sudden unexplained death in epilepsy.
- ☆ Adjacent normal heartbeat interval differences exceeding pNN50: The deviation of adjacent normal heartbeat interval differences beyond pNN50 is closely associated with parasympathetic nervous system activity and is related to RMSSD and HF power. However, RMSSD typically provides a better assessment of parasympathetic nervous system activity (especially in the elderly). Therefore, most researchers tend to choose RMSSD over the adjacent normal-to-normal heartbeat interval differences exceeding pNN50.

### 2. Frequency Domain Indices

- Low frequency (LF) : The low frequency (LF: 0.04-0.15 Hz) reflects the mixed activity of the sympathetic and parasympathetic nervous systems. In certain situations, LF can be used to assess the influence of the sympathetic nervous system, but this requires consideration of respiratory and other physiological influencing factors.
- ☆ High frequency (HF) : The high frequency (HF: 0.15-0.4 Hz) primarily reflects parasympathetic nervous system activity, especially vagal nerve activity. This can be observed through Respiratory Sinus Arrhythmia (RSA).
- ☆ LF/HF ratio : The LF/HF ratio is used to assess the balance between the sympathetic nervous system and the parasympathetic nervous system.

